## 8.6 Vulnerable Populations

**TABLE 1:** Vulnerable populations included and excluded from this study:

Include	Exclude	Vulnerable Population Type
	x	Adults unable to consent
	x	Individuals who are not yet adults (e.g. infants, children, teenagers)
	x	Wards of the State (e.g. foster children)
	x	Pregnant women
	x	Prisoners

No vulnerable populations will be enrolled. A key inclusion criterion is that participants need to be cohabiting with a significant other and have daily contact. As most children aged 17 or under are not emancipated, few children would be eligible for this study. Pregnant women will be excluded since the primary outcome of this study is long-term weight loss, and weight loss is contraindicated during pregnancy. Prisoners will be excluded as per the OHRP guidelines. Prisoners would not have daily contact with their study partner or the flexibility in dietary and exercise choices compared to the general population.

### 8.6.1 Participant Capacity

All participants will have the capacity to give informed consent.

### 8.6.2 Participant/Representative Comprehension

To ensure comprehension, after hearing and reading about the study, the participant will be asked to summarize the study and the requested activities for participation in the study. The investigator or research staff will then ask the participant if anything could be clarified before consent is obtained.

Decisionally impaired adults are excluded from this study.

## **8.7 Informed Consent**

The PI will be responsible for ensuring that valid consent is obtained in person and documented for all participants.

The activities involved to review the EMR for potentially eligible participants are considered “preparatory to research” and will be conducted by the Clinical Research Data Service or the Department of Surgery Data Analysis & Reporting Team. The Department of Surgery Data Analysis & Reporting Team will pull the data once they have the necessary approvals. Individuals will be directed to go to an online screening website or they might be contacted directly by phone by the study team if individuals do not opt-in or opt-out on their own.

Individuals and their partners who are interested in participating will be instructed to go to an online screening website which will determine their initial eligibility. For those who are potentially eligible, an in-person (or remote) screening/enrollment visit will be scheduled. The screening/enrollment visit will be divided up into two parts. The first part of the visit will determine the patient’s final eligibility by collecting the following measurements: height, weight, cognitive screen, and reconfirmation that they are not pregnant (females). For the partners, height, weight and cognitive screening measurements will be completed to determine their final eligibility. If the visit is done remotely, height and weight will not be collected. Once the patient and partner meet the final eligibility measurements, they will be asked to provide written consent (or oral consent if the screening/enrollment visit is done remotely) and complete the rest of the baseline measurements. The consent process will consist of a detailed verbal description of the study including its risks, potential benefits, and requirements. Potentially eligible participants and their partner will be given an IRB-approved/stamped informed consent form with all required elements and factual correctness to read, then ample time to read and reflect on participating. If the individual and/or partner requests, they will be given additional time to consider participation, including re-scheduling the screening visit. Before obtaining consent, each individual and their partner will be allowed to ask questions until a decision can be made by either party. When ready, participants and their partner will be required to sign the consent form (or oral consent will be obtained if the screening/enrollment visit is done remotely). Study audits by the PI will include review of consent documents for signatures and use of the IRB date-stamped form to ensure compliance.

### **8.7.1 Process of Consent**

Members of the WREN staff will be responsible for obtaining consent. The written/signed consent (original copy) will be stored in a locked file cabinet, in a locked office with the research team.

The process of informed consent will be structured to be conducive to rational and thoughtful decision making by the patient and their partner – including time for discussion, questions, and the ability to reschedule if additional time for consideration is needed. Legally authorized representatives will not be allowed to sign the consent; patients who require legally authorized representatives are excluded from the study.

Auditors, witnesses, and translators will not be part of the consent process. Non-English speakers are excluded from the study. Additionally, patients who are unable to read or write in English (*i.e.*, illiterate) are excluded.

### **8.7.2 Consent to Participate in Research and Authorization to Use Protected Health Information for Research Form**

**See Attachment for Consent to Participate in Research and Authorization to Use Protected Health Information for Research Form**

Signed consent and HIPAA authorization (or oral consent if the screening/enrollment visit is done remotely) will be obtained from the patients and their partners arriving for the screening visit once their final eligibility requirements have been met. Patients and partners will be given adequate time to review the document and ask any questions they have. A copy will be given to the patient and their partner that signed the form, on the same day they each sign the form.

Information about study participants will be kept confidential and managed according to the requirements of the Health Insurance Portability and Accountability Act of 1996 ([HIPAA](#)). PHI that will be collected from participants includes name, address, telephone numbers, Medical Record Number, e-mail, date of birth, web addresses and internet protocol addresses.

### **8.7.3 Revoking Consent**

In the event that a participant revokes authorization to collect or use PHI, the investigator, by regulation, retains the ability to use all information collected prior to the revocation of participant authorization. For participants that have revoked authorization to collect or use PHI, attempts will be made to obtain permission to collect at least vital status (i.e. that the participant is alive) at the end of their scheduled study period.

### **8.7.4 Costs to the Participant**

Participants will not have to pay for any study procedures or materials including the Fitbit™ watch that will be used. The patient will not be billed by their healthcare system or their health insurance company for any costs related to a study procedure.

Participants will be responsible for any costs if they require any follow-up procedures with their primary care physician, including all out-of-pocket costs.

### **8.7.5 Payment for Participation**

Payments to patients and partners will be provided as the study progresses; participants do not have to complete the entire study to receive a payment.

All patients and their partners can receive a remuneration up to \$180/each (\$360 for the couple) for completing all outcome assessments. For each of the Month 6, 12 and 18 month completed assessments, patients and their partners will receive \$40/each (\$80 for the couple). The payment will increase to \$60 for completion of the final assessment (\$120 for the couple) due to the importance of collecting the primary outcome data at this visit.

Month 6: \$40 each/\$80 per couple

Month 12: \$40 each/\$80 per couple

Month 18: \$40 each/\$80 per couple

Month 24: \$60 each/\$120 per couple

The remuneration will acknowledge their time and study participation, not behavior change. Additional payment will not be available to participants for travel or other costs (example: childcare) that are incurred.

## **8.8 Early Withdrawal of Participants**

### **8.8.1 Premature termination of study**

This study may be temporarily suspended or prematurely terminated if there is sufficient reasonable cause. Written notification, documenting the reason for study suspension or termination, will be provided by the suspending or terminating party to all site investigators, funding agency, DSMB (i.e., ICTR DMC), and IRB. If the study is prematurely terminated or suspended, the PI will promptly inform the IRB and will provide the reason(s) for the termination or suspension.

Circumstances that may warrant termination or suspension include, but are not limited to:

- Determination of unexpected, significant, or unacceptable risk to participants
- Insufficient compliance to protocol requirements
- Data that are not sufficiently complete and/or evaluable

Study may resume once concerns about safety, protocol compliance, data quality are addressed and satisfy the funder, IRB and/or DMC. All participant data that were collected prior to study termination will be analyzed and continue to be handled/stored per this protocol.

### 8.8.2 When and How to Withdraw Participants

Participants will be educated on the consent form that they are able to withdraw at any time without adverse effects. Participants may withdraw by alerting study staff in person, by telephone, or by email. If participants withdraw from the study, then their status will be updated in the tracking database, and no further contact will be made. Participants may be withdrawn at the discretion of the PI for safety reasons (e.g., self-report of pregnancy) or because they cannot participate meaningfully in the intervention (e.g., cannot communicate well by telephone). These individuals will be informed by study staff in person or by telephone that their participation has ended and the reason for ending their study participation. Their status will then be updated in the tracking database, and no further contact will be made.

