To enhance recruitment, we will do the following: discuss the study directly with partners to address any questions/concerns; frame weight loss as a couples' issue in recruitment materials; emphasize potential benefits of the intervention and outcome assessments to partners; offer sessions at different times of day; and offer two sessions that address communication to couples in the patient-only arm following the 24-month assessment. If partners no longer wish to receive intervention, then we will retain patients in the intervention (intent-to-treat analyses). If patients no longer wish to receive the intervention, then partners will no longer receive the intervention either. In such cases, we will ask patients (and partners) to return for outcome assessments, as we have done in our previous trials. Other efforts to maximize retention for outcome assessments include: administer the ASA24 online; e-mail/text reminders one week prior to the beginning of each window; place telephone calls and mail letters if participants are non-responsive to electronic reminders; compensate patients and partners \$40 each for completed interim assessments; and increase payments for the final assessment (\$60 each), as we did in the

MAINTAIN trial. In the MAINTAIN trial, 85% of patients returned for final assessments; in the CouPLES trial, 88% of patients and 70% of spouses did.(42, 50)

No participant will be excluded on the basis of race or sex. There have been mixed findings regarding the moderating role of sex in couples-based weight loss interventions. Failure to balance arms with respect to sex could, therefore, affect outcomes. Sex is explicitly accounted for in the study design in that it is a stratification variable. This variable, along with the other stratification variables of patient BMI and partner BMI, will be included in the statistical models for the primary outcome of weight, secondary outcomes of diet and physical activity, and mediation analyses.

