### 8.8.3 Data Collection and Follow-up for Withdrawn Participants

If partners no longer wish to receive intervention, then we will retain patients in the intervention. If patients no longer wish to receive the intervention, then partners will no longer receive the intervention either. Regardless of whether partners or patients request not to receive further intervention, we will ask patients and partners to return for outcome assessments. Patients who attend the first group session (i.e., provide a baseline weight) will be considered randomized and will be analyzed according to intent-to-treat principles, regardless of further intervention adherence; these individuals will not be replaced if they drop out subsequent to the first session. Consented participants who do not attend the first session (i.e., do not provide a baseline weight measurement) will not be considered randomized and thus will be replaced.

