Patients and their partners will return for outcome assessment visits at month 6, 12, 18 and 24 (Table 2). These outcome assessment visits may occur remotely via a video conference if necessary due to public health safety measures. For the patients, at months 6, 12 and 18: weight, dietary intake, physical activity, transformation of motivation, couples' efficacy, outcome efficacy, use of communal coping, social support for diet and physical activity, brief pain inventory-short form and COVID-19 will be measured by using the previously described methods. Additionally, at months 6, 12, 18 and 24, patients will complete a weight loss methods survey to see if there are any other ways they attempted to lose weight other than being in the study. For the transformation of motivation, couples' efficacy, outcome efficacy, use of communal coping, social support for diet and physical activity, brief pain inventory-short form, weight loss methods, and COVID-19 surveys, these will be sent ahead of their visits as a REDCap link via text and/or e-mail. The surveys will be completed at the outcome assessment visit if patients and partners do not complete them ahead of time, on their own. At month 24: weight, surveys (weight loss methods and COVID-19), dietary intake and physical activity assessments will be obtained. For the partners, all of the same measurements will be obtained at the same time-points except for physical activity. All outcome assessment visits will be completed by the WREN Research Coordinators. If patients or partners are unable to attend an in-person outcome assessment visit due to illness or public health safety measures, then we will collect their self-reported weight photos via a DOS REDCap link.

At months 3, 9, 15 and 21, transformation of motivation, couples' efficacy, outcome efficacy, use of communal coping, social support for diet and physical activity, and COVID-19 will be measured for both patients and partners. Patients and partner will be sent the surveys as a REDCap link via text and/or e-mail.

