#### **Patient weight loss maintenance intervention (months 7-18, both arms)**

Patients will transition to the behavioral maintenance intervention in month 7 regardless of whether they achieved their 6-month weight loss goal for 3 reasons: 1) It is not feasible for some patients to continue the group-based initial protocol while others transition to the individual maintenance protocol; 2) Based on previous studies, most patients achieve maximum weight loss at 6 months; 3) Our maintenance protocol allows for patients to continue pursuing weight loss during the maintenance phase if desired. The protocol also stipulates that patients who relapse (gain > 3lb.) should revert to creating dietary and physical activity goals and monitoring these behaviors, thus re-focusing on weight loss. In months 19-24, patients will not receive intervention but will be encouraged to continue self-monitoring using the provided devices. This transition mimics real-world practice in which patients would be expected to apply the maintenance skills they have learned once intervention contacts cease. The 6-month period without intervention contact will allow examination of the sustainability of intervention effects.

The maintenance intervention was designed to help patients transition from the intensity that characterizes most weigh loss interventions to the real world in which patients rarely have further intervention-related contact. This intervention involves a shift from diet initiation content to maintenance-oriented skills training, then switches mode from in-person to telephone, and finally decreases contact frequency. The interventionist will place all telephone calls using a semi-structured script programmed into a custom intervention program that records participant responses for reference in subsequent calls. There will be a 2-week window around the target call date. If the educator is unable to contact a patient in the call window, then that telephone call will be skipped. Continuity will be maintained because each call involves a review of data from the previous call and a review of the same behavioral skills. All maintenance telephone calls will be audio recorded. [name] will meet with [name] and the interventionists weekly to review a random subset of recorded calls and provide feedback using a checklist.

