**Aim 1: Test the hypothesis that average patient weight is at least 2.5 kg lower in the partner-assisted arm than the patient-only arm at 24 months.** The unit of time will be months relative to randomization. The outcome is weight measured at each in-person study visit. Therefore, *month0* represents the weight at the point of randomization (i.e., the first group visit), and *month24* represents the primary study endpoint. The between-arm comparison in net weight loss from *month0* to *month24* will be examined with a multilevel longitudinal model(80) of the general form:  $Y_{ijt} = X_{ijt}\beta + c_j + Z_{ijt}b_{ij} + \varepsilon_{ijt}$ , where  $Y_{ijt}$  is weight in kg for patient  $i$  in small group  $j$  at  $t=month0, 6, 12, 18, 24$ . The predictors in the model will ( $X_{ijt}$ ) include a time main effect, the intervention main effect, and the intervention arm by time interaction, and  $Z_{ijt}$  will include an intercept and a time effect. We will use a flexible polynomial model for the main effect of time and keep the treatment by time interaction linear in time. We will first explore cubic time effects. If it is inadequate for the complexity in the temporal trend, higher order polynomials will be explored. We will formally check for the adequacy of a particular form for time effects using Wald or likelihood ratio tests for higher-order terms. The effect  $c_j$  is an additional random intercept for small group  $j$ , capturing common effects at the small group level. The predictor vector  $X_{ijt}$  will also include indicator variables for each of the eight strata defined by the cross-classification of the stratification variables of patient sex, patient BMI, and partner BMI. As a first step, the correlation of patients' repeated measures over time will be modeled and accounted for via the patient-level random intercept and time slope,  $b_{ij}$ . However, as is advised by good modeling practice,(80) various covariance structures for time will be explored, including unstructured and differential correlation structures by arm, via graphics such as the variogram and estimation with ReML,(81) all while being blinded to treatment effects. The AIC and BIC fit indices will be used to choose the best correlation structure. We will estimate the parameters in the model using the SAS procedure MIXED (Cary, NC). To test the null hypothesis that the average weight is equal in the two intervention arms, we will test if the coefficient for the time by treatment interaction is zero. Specifically, if  $X_{ijt}\beta$  takes the following form  $\beta_0 + \beta_1 trt + \beta_2 time + \beta_3 trt * t + \beta_4 covariates$ ,

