### 10.3 Participant Population(s) for Analysis

All participants' data will be analyzed, using an intent-to-treat approach. The sample size justification appears in Section 8 Study Participants.

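### Section 8.8.2 ends all contact with a patient the PI withdraws as unable to take part meaningfully in the intervention, and Section 8.8.3 does not clearly restore outcome follow-up, so an obtainable month-24 weight could be lost

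*Combined protocol and SAP*

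**What the plan says.** Section 8.8.2 gives the PI discretion to withdraw participants for safety reasons or "because they cannot participate meaningfully in the intervention (e.g., cannot communicate well by telephone". Staff tell them that their participation has ended and why. The section then says: "Their status will then be updated in the tracking database, and no further contact will be made". It makes no exception for outcome assessments.

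Section 8.8.3 follows directly and is headed as covering data collection and follow-up for withdrawn participants. It says: "Regardless of whether partners or patients request not to receive further intervention, we will ask patients and partners to return for outcome assessments". Section 8.5.1 deals with patients or partners who no longer want the intervention and says: "In such cases, we will ask patients (and partners) to return for outcome assessments, as we have done in our previous trials".

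Section 8.8.3 also commits to analysing every patient who attended the first group session by intent-to-treat, whatever their later adherence, and does not replace those who drop out after it. Section 10.3 adds: "All participants' data will be analyzed, using an intent-to-treat approach". Section 13.4 says that noncompliance is not a reason to exclude anyone from the study or the analyses. Section 7.1.1 defines the primary outcome as patient weight at 24 months.

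**The concern.** The withdrawal ground concerns the intervention, but its consequence is the end of study contact. A patient who communicates poorly by telephone can still stand on a scale. If staff apply Section 8.8.2 as written, the later weights are not collected, for a reason unrelated to consent, safety or the ability to be weighed.

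The sections are also uneven. A patient who declines further intervention is asked back for assessments. A patient whom the PI judges unable to take part in it is, on the literal text, not contacted again. The documents give no reason for the difference. What is at stake is the completeness of the primary endpoint in randomized patients, which Section 8.7.5 treats as important enough to justify a higher final payment.

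**Working it through.** The plan states no figure on this point, so the check sets the passages side by side and then counts what could be lost.

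**1. Can the ground apply after randomization?** Yes. Under Section 8.8.3 a patient counts as randomized on attending the first group session. Individual telephone calls run in months 7-18 (Section 2; Section 9.2.2, Table 3). The protocol's own telephone example therefore falls mainly after randomization.

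**2. Does another section restore follow-up?**
- For participants who act themselves, the protocol separates two cases. Leaving the study ends contact (8.8.2). Stopping only the intervention leads to an invitation to return (8.5.1, 8.8.3).
- For withdrawal by the PI on this ground, no such line is drawn. The reason concerns the intervention, and the result is the end of the study.
- Section 8.5.1 is confined to people who no longer wish to receive the intervention.
- Section 8.8.3 can be read in two ways. If its return-visit sentence covers only people who ask to stop, it does not reach PI withdrawals. If it covers everyone, it asks for return visits from people with whom Section 8.8.2 forbids contact. Either way the two sections need reconciling.
- Section 12.5.1 repeats the right to withdraw participants and says nothing about later assessments.

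**3. What could be lost?** The Aim 1 model in Section 10.2 uses weights at months 0, 6, 12, 18 and 24. Section 8.7.5 pays $40 each at months 6, 12 and 18 and $60 at month 24.

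| Time of withdrawal | Weights already taken | Weights that could be lost | Payments for the remaining assessments, per person |
|---|---|---|---|
| Between months 0 and 6 | 0 | 6, 12, 18, 24 (4 of 5) | 40 + 40 + 40 + 60 = $180 |
| Between months 6 and 12 | 0, 6 | 12, 18, 24 (3 of 5) | 40 + 40 + 60 = $140 |
| Between months 12 and 18 | 0, 6, 12 | 18, 24 (2 of 5) | 40 + 60 = $100 |

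Month 24 is in the lost set each time. Withdrawal on this ground after month 18 scarcely arises, because intervention contact has ended by then.

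**4. Does the analysis make up for it?** In part. Scheduled weights taken before withdrawal stay in the mixed model, which is fitted with this time structure: "We will use a flexible polynomial model for the main effect of time and keep the treatment by time interaction linear in time". Earlier weights therefore still inform the tested coefficient. Group weigh-ins from months 1-6 are not in that model; they could enter only through the sensitivity imputation, which Section 11.2.2.1 builds on all observed weights. Neither route supplies the month-24 weight itself.

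**The case against.** The best reply is that Section 8.8.3 is the specific rule. Its heading names withdrawn participants, and its opening words, read literally, take in people who made no request to stop. Section 13.4 points the same way. This reading is defensible, and because of it one can say only that weights could be lost, not that they will be. It does not remove the problem: the same reading puts Section 8.8.3 in direct conflict with the no-contact sentence, and staff need to know which to follow.

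The second reply is rarity, and it stands. The ground is discretionary. Trouble reaching a patient does not by itself trigger it: "If the educator is unable to contact a patient in the call window, then that telephone call will be skipped". Impaired hearing is an exclusion (8.3), and English and a cognitive screener score are required (8.2). Such losses may also fall within the 20% attrition already allowed for in Section 10.1.

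A reader might go further in three ways that the documents do not support.
- **That these patients are dropped from the analysis.** They are not. Their earlier weights are kept, and the gap is in collection only.
- **That the primary result is biased or the trial underpowered.** The documents give no rate of such withdrawals and no imbalance between arms, so no figure can be derived.
- **That the stopping rules in Section 12.5.1 need rewriting.** That section does not list this ground, and the point does not extend to it.

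**Conclusion.** The concern holds in limited form. Sections 8.8.2 and 8.8.3 do not fit together for patients whom the PI withdraws as unable to take part meaningfully in the intervention. If Section 8.8.2 is followed literally, two to four of the five scheduled weights, always including month 24, could go uncollected for each such patient, depending on when withdrawal occurs. This sits badly with the intent-to-treat and noncompliance statements.

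The number of patients is unknown and probably small, and no effect on bias or power is claimed. The conclusion rests on the protocol text; the attachments listed in Section 18, which include the consent form, were not available for this check and may say more. This is a cheap improvement worth making, not a flaw that threatens the trial.

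**What to change.** - **Section 8.8.2, for this ground only:** separate stopping the intervention from leaving the study. Keep inviting these patients to the remaining scheduled outcome assessments unless they withdraw consent to follow-up. Use the existing visit procedures, with photo weights only in the situation that Section 9.2.1 already names: "If patients or partners are unable to attend an in-person outcome assessment visit due to illness or public health safety measures".
- **Section 8.8.3:** state that it covers this ground.
- **Records and reporting:** record the reason and date of each such withdrawal, and report counts by arm.

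Leave unchanged the grounds for stopping the intervention, the safety and pregnancy rules, and Section 12.5.1.

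The cost is a few sentences of protocol text, a few extra visits, and assessment payments of at most $180 per person under the existing schedule.
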